4.4 Recruitment Procedures

Formative Work: Participants will receive a \$25 gift card to participate in focus groups and playtesting sessions. Flyers will be circulated throughout schools.

Pilot Study: For the pilot study, participants will receive a \$25 gift cards as compensation for completion of assessments at each time point. We will share with educators, school-based providers, and our youth advisory board who will share with students. Students may then share with other students (e.g., snowball sampling). The flyers contain a QR code for students to input their first/last name, phone number, and email address. If they are younger than 18, they must input parent/guardian first and last name, phone number, and email address. Research staff will then contact them to obtain consent/e-consent. When needed, study staff will be available to parents/guardians for information sessions should they have any questions.

4.5 Risks

The potential risks associated with this study have to do with maintenance of the confidentiality of the identities of the participants enrolled in the study and information relating to them. As with all of our studies, we will train study researchers in maintaining

confidentiality. Prior to the start of the focus groups, researchers will discuss potential risks including breach of confidentiality.

Given engagement in discussions with the research team about its content may pose a potential psychological risk in that we address sensitive issues around mental health, substance use, and its consequences, [name] (who is a Certified School Counselor and Licensed Professional Counselor, and has extensive expertise working with adolescents, college-aged youth, and schools) will be on site for all study sessions in Miami and Connecticut with research staff, when available, to connect participants to school-based personnel as a resource should any distress or concern arise. [name] has a long-standing relationship with school partners and will refer students to their school-based personnel for additional support.

If there are additional concerns raised with regards to active substance use or mental health, or if participants need additional or more intensive attention, the research staff will seek medical advisement from Dr. [name], a medical doctor with expertise in addiction medicine, or Dr. [name], a psychiatrist. All students will receive resources for support and hotline information from NIDA and NIMH. Students who report moderate to high suicide risk and/or depression will be directly connected immediately to the on-site school-based provider who will follow their school's protocol to help navigate care or file a referral (examples include conducting a safety planning intervention, connecting to outpatient clinic, notifying parent/guardian, and/or contact with local crisis intervention team and transport via ambulance to local emergency department as deemed necessary). Students will be flagged by our RedCap system as moderate-/high-risk as a result of their answers on the PHQ-8, GAD-7, CHRT, or ASQ measures, which will result in an immediate email notification to research staff on site who will immediately refer or connect the student to the on-site school-based provider.

If a student indicates moderately severe to severe symptoms of depression, student will be flagged and immediately connected to the school-based provider for a risk assessment and follow school protocol. If student is cleared by the school social worker, student may continue in the study and the school social worker will follow up with student in two weeks.

If a student screens positive for suicide (but is not acutely suicidal), student will be flagged and immediately connected to school-based provider for a risk assessment and follow school protocol. If student is cleared by school social worker, student may continue in study and the school social worker will follow up with student in two weeks. If student is acutely suicidal, student will be flagged and immediately connected to school-based provider who will follow school protocol (e.g., contact 211, contact parent/guardian, etc.). They will be ineligible to participate in the study on this day. Student may not return to rescreen for participation for at least 2 weeks and only when they are no longer actively suicidal. Eligibility for rescreening will be based on the resolution of the moderate or severe suicidality and may include being on active treatment, clearance by the school social worker according to school policy, or completion of brief treatment. Documentation of the resolution of the acute suicidality state will be documented upon assessment for eligibility for rescreening.

If any student were to become triggered as a result of the sensitive nature of the topics, the school-based provider will be able to offer and/or refer to school-based emotional support and/or referral services. The school-based provider will not be a part of handling any of the research protocols; however, the provider will be present and available for support services, as needed. They will receive a \$75.00 gift card for their time.

This study presents minimal risks to the participants and adverse events or other problems are not anticipated.

Adverse Events (AEs):

Violation of confidentiality: Any breach of confidentiality.

Discomfort due to assessment procedures: Discomfort created by answering survey questions. Embarrassment in disclosing sensitive personal information.

Disclosure of information about current and/or intended physical harm to persons; current and/or intended abuse of children that would be reported to a child welfare agency; and/or an investigation of such allegation(s) that could ensue.

Dissatisfaction with the game activities: In this case it would be the gameplay experience. While gaming addiction is a recognized entity, it is very rare and, in the setting of playing a serious game, very unlikely. If there are any concerns of developing serious addictive behaviors in our pilot study participants, we have team members who are experts in the field of addiction medicine and will address these issues immediately.

Serious Adverse Events (SAEs):

SAEs include death, life threatening injury or condition, hospitalization, persistent or significant disability/incapacity, and other conditions which in the judgment of the investigators represent significant hazards. In the rare event of an SAE, we do not expect them to be related to our study.

Procedures for research team management of AEs, SAEs and other study risks such as mandatory reporting requirements:

This study presents minimal risks to the participants and adverse events or other problems are not anticipated. In the unlikely event that such events occur, Reportable Adverse Events (which are events that are serious or life-threatening and unanticipated (or anticipated but occurring with a greater frequency than expected) and possibly, probably, or definitely related) or unanticipated problems involving risks to subjects or others will be reported in writing within five calendar days to the IRB (using the appropriate forms from the website and electronic submission system) and the NCATS PO. The PI will apprise fellow investigators and study personnel of all adverse events that occur during the conduct of this research project through regular study meetings and via email as they are reviewed by the PI. We will use procedures to detect and respond to adverse events that ensure prompt discovery of any adverse events and to minimize their effects. There is adequate surveillance and protections to discover adverse events promptly and keep their effects minimal.

Procedures for training and supervision of all research personnel have been developed as part of our previous and current studies. All members of the research team are familiar with procedures for identifying and reporting possible adverse reactions. All members of the research team are trained in mandatory reporting and will notify the PI immediately of any concerns raised about participant mental health (suicidality), substance use, abuse of any kind, and so forth.

If an adverse event occurs study personnel will notify the PI as well as the appropriate Information Security Officer (ISO) and follow all necessary procedures. All adverse events are reported using the Yale Institutional Review Board (IRB) standard template for reporting adverse events. The PI reviews all adverse events, classifies the attribution of adverse events (e.g., definitely, probably, possibly related; unlikely or unrelated) and grades the severity of the event, utilizing the FDA's definition of serious adverse events, on a 6-point scale (0=no adverse event or within normal limit; 1=mild; 2=moderate; 3=severe; 4=life-threatening; 5=fatal). Serious unanticipated or anticipated adverse events will be reported promptly to the IRB within five calendar days and to the NCATS PO within 24 hours by phone and/or email and will submit a written report to the PO no more than two days later.

The PI will evaluate all adverse events and determine whether the event affects the Risk/Benefit ratio of the study and whether modifications to the protocol (e.g., Risks to Subjects) or consent form (e.g., Risks and Inconveniences) are required.

The PI will be responsible for monitoring the data and conducting performance and safety reviews, at the specified frequency. Either the PI or the IRB have the authority to stop or modify the study. The monitoring by the IRB will occur annually at the time of re-approval. The PI will conduct data and safety review at least quarterly and at any time a serious adverse event occurs. During the review process, the PI will evaluate whether the study should continue unchanged, requires modification or amendment to continue, or should be closed to enrollment.

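### New or worsening suicidality is not named as an adverse event, and no count by arm of participants who develop it is planned

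*Combined protocol and SAP*

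**What the plan says.** Section 4.5 (Risks) lists four adverse events:

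- "Violation of confidentiality: Any breach of confidentiality"
- "Discomfort due to assessment procedures: Discomfort created by answering survey questions", with embarrassment at disclosing personal matters
- "Disclosure of information about current and/or intended physical harm to persons; current and/or intended abuse of children", worded around reports to a child welfare agency and any investigation that follows
- "Dissatisfaction with the game activities: In this case it would be the gameplay experience"

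It then defines serious events: "SAEs include death, life threatening injury or condition, hospitalization, persistent or significant disability/incapacity, and other conditions" that the investigators judge to be significant hazards. The section also states: "This study presents minimal risks to the participants and adverse events or other problems are not anticipated".

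Suicidality is handled elsewhere, in two ways. The first is clinical. "Students will be flagged by our RedCap system as moderate-/high-risk as a result of their answers on the PHQ-8, GAD-7, CHRT, or ASQ measures", and the consequence in sections 4.5 and 6.4 is connection to the on-site school provider. Team members "will notify the PI immediately of any concerns raised about participant mental health (suicidality), substance use" (repeated in 9.1). A student who screens positive but is not acutely suicidal may stay in the study once cleared.

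The second is as an outcome. Sections 6.1, 6.4 and 6.8 include the CHRT-SR and ASQ. Section 7.2 compares severity of suicidal ideation and attempts, and fits a mixed model of game against control over baseline, post-game and 3 months. The hypothesis is a decrease relative to control, and all of these analyses are labelled exploratory.

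**The concern.** The game is about suicide prevention, and section 4.5 itself recognises a psychological risk from the sensitive content. New or worsening suicidality is therefore the harm a later investigator would most want to see counted. A student who is unflagged before play, has a non-serious positive ASQ or CHRT screen afterwards, and is referred and cleared does not clearly fit any of the four listed AEs and need not meet the SAE definition.

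This matters because attribution, severity grading, IRB-template reporting and the risk/benefit evaluation in section 4.5 apply to events once they are recognised as adverse events. Referral and notification look after the student. They do not create an AE record, and section 7.2 asks for no table that would bring the records together by arm. The pilot could report no adverse events while its own database holds new flags, and later work would then start from an incomplete safety record.

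**Working it through.** The plan states no figure on this point: no suicidality rate, dropout rate or power. The check is therefore mainly of the text, with some arithmetic for scale.

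**1. Does any listed event cover the case?** None of the four AE items names suicidal ideation or behaviour. One, physical harm to persons, could be read to include disclosed self-harm. The SAE definition would take in a suicide death, a life-threatening attempt, a hospitalization, or anything the investigators judge a significant hazard. The uncovered case is non-serious new or worsening ideation.

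**2. Does any rule turn a flag into an AE?** Flag consequences in 4.5 and 6.4 are an email to site staff, referral and follow-up by the school. The duty to notify the PI (4.5, 9.1) concerns suicidality as a matter to raise; neither section says that it is recorded or graded as an AE.

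**3. Is there a count by arm?** Section 7.2 plans no tabulation of AEs, SAEs, referrals or new flags. Section 7.6 names no safety events for the DSMB to review.

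**4. Does the score comparison in 7.2 do the same job?** It would show an average shift in either direction. It need not show worsening in a few students. Illustration with assumed changes: 3 of 30 students worsen by 8 points and 27 improve by 1.

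Mean change = (3 × 8 − 27 × 1) / 30 = (24 − 27) / 30 = −0.1

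The arm appears slightly improved although 3 students deteriorated. If CHRT-SR items are summed (14 items scored 1 to 5), the total runs from 14 to 70, so a change of 8 is possible.

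**5. What could counts show at 30 per arm (sections 5.3 and 6.1)?**

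- Upper limit with no events: 1 − 0.025^(1/30) = 11.6% (exact, two-sided 95%).
- Chance of at least one event in an arm, 1 − (1 − p)^30, at assumed true rates:

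| True rate p | P(at least one in 30) |
|---|---|
| 1% | 26% |
| 2% | 45% |
| 5% | 79% |
| 10% | 96% |

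- Fisher exact test with no events in control: 5 against 0 gives p = 0.052; 6 against 0 gives p = 0.024. For assumed true rates of 5% and 20%, its power is 24%.

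Counts with intervals are informative at this size. A significance test is not.

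**The case against.** The strongest reply is that suicidality is already covered. It has several parts.

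- **It is compared by arm.** This stands. A reader might infer that suicidality is never compared between groups, but section 7.2 does compare ideation and attempt scores, and average worsening in the game arm would be visible there. What it lacks is a participant-level count.
- **Serious events are captured.** This also stands. A reader might infer that no suicidal event could ever be recorded; the SAE definition and its judgment clause do not support that. Nor does the AE list say it is exhaustive, and the PI is to review and grade all adverse events from mild to fatal. Even so, nothing tells the PI that a non-serious new flag is one of them, and two staff members could classify the same student differently.
- **The PI is notified, reviews safety at least quarterly, and a DSMB is planned.** True, and it lowers the risk that events go unseen. It does not define what is counted.
- **The timing is uncertain.** A reader might assume that ASQ and CHRT are given at every assessment. The plan has three assessment times but no schedule by instrument, and section 6.8 places the Brief COPE at baseline and 3 months only. Section 6.8 also heads the ASQ as covering the past 30 days. Repeated straight after a game of about 45 minutes, it would cover almost the same period, so a new positive could reflect changed reporting. The fix must allow for this.
- **Sixty participants are too few.** That rules out a test, not a table.

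**Conclusion.** The point holds in a limited form. Non-serious new or worsening suicidality has no assured route into the AE record, and no participant-level safety count by arm is planned. The documents do not show that a wrong safety conclusion will follow: an alert PI could record such events, and the score comparison would show a mean shift. They show that the plan, followed as written, permits a report of no adverse events alongside new flags in REDCap.

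How many participants would be affected is unknown, because no rate is given. The 11.6% limit assumes that all 30 in an arm are assessed; losses by 3 months would widen it. The rates and score changes in the working are assumptions for scale, not estimates for this trial. This is a cheap improvement to an exploratory pilot rather than a flaw in its primary aims of usability, acceptability and feasibility.

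**What to change.** **Section 4.5, AE list.** Add new or worsening suicidal ideation or behaviour, defined from the existing instruments at whichever post-baseline assessments they are given:

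- for a participant not flagged at baseline, an ASQ or CHRT flag that was absent at baseline;
- for a participant flagged at baseline and cleared to continue, a newly endorsed ASQ item, or an increase in the CHRT Suicidal Thoughts score by a margin fixed before data review.

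The second part is needed because a definition based only on new flags would miss worsening in students who entered with a positive, non-acute screen. State which instruments are given at each assessment, and the REDCap flag threshold in use, so that the definition can be applied.

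**Section 7.2.** Add a descriptive table by arm, with exact 95% confidence intervals and no hypothesis test, of participants with new flags, worsening, referrals, AEs and SAEs. Show the number assessed at each time as the denominator.

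Leave the referral and clinical steps as they are; this concerns recording and reporting only.

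**Cost.** One definition and one small table from data already collected. More AEs will be recorded, some reflecting changed reporting rather than an effect of the game. Showing the control arm alongside helps the reader judge how many.

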4.6 Anticipated Benefits

The study may have no direct benefits to the participants, but may help researchers find out something that will help educators, clinicians, and/or adolescents.

4.7 Vulnerable Populations

Given participants will include minors (aged 13 through 17) who will participate in focus groups, information sheets will be shared prior to enrollment with minors and their parents/guardians.

For the pilot study, adolescent assent and parent/guardian consent/e-consent will be required for minors.

4.8 Consent/Assent Procedures

Formative Work: Given our study focuses on prevention and aims to better understand perceptions of peers and students, this protocol is eligible for a waiver of documentation of consent. The study will be introduced to parents/guardians and students and then, if interested in participating, information sheets will be provided via paper form or electronically. For participants under the age of 18, parents/guardians who do not wish for their children to participate will communicate disapproval to the research staff or remain silent/walk out for the purpose of demonstrating no interest to participate without

communicating to staff. Both options will result in non-participation by the adolescent. If COVID-19 restrictions apply, we may modify this process and share flyers with educators who will share with their students and/or parents/guardians. No forms will be signed in our procedures. This protocol is one we have used in our previous qualitative work and has been approved by the Yale IRB.

Pilot Study: For the pilot study, we will obtain informed written or digital consent from adolescents above the age of 18 and informed written or digital consent from parents or guardians with adolescents under the age of 18. We will obtain informed written or digital assent from all participants. We will share flyers with educators, school-based providers, and our youth advisory board who will share the flyer with students. Students may then share with other students (e.g., snowball sampling). The flyer contains a QR code where students will input their first/last name, age, grade, and email address and parent/guardian first and last name, phone number, and email address. Research staff will then contact them to obtain consent/e-consent. When needed, study staff will be available to parents/guardians should they have any questions.

5 - Methods

Pilot Study: Treatment – Device

5.1 Intended Use for Device (provide the following information for each device being investigated in the study)

supportED is a digital prevention game focused identifying warning signs, coping strategies, and resources for seeking help. The overall goal is to prevent suicide in youth who may be at risk due to substance misuse. The formative work of this game included focus groups and playtesting to develop a prototype of the game. In the subsequent pilot study, we will be investigating the usability/ feasibility of delivering the game in schools. This is not a pivotal study, as it is not powered to demonstrate efficacy of the game (n=60). For this reason, preliminary outcomes will only be exploratory in nature. Given the preliminary nature of the research, and primary outcomes of usability, feasibility, and acceptability we anticipate supportED to be classified as a non-significant risk device.

supportED is not designed to be a replacement for or of substantial importance in diagnosing, mitigating, or treating mental health, substance misuse, and suicidal thoughts and behaviors in youth. It is an external web-based game that does not present potential for serious risk. supportED models the process of a safety planning approach, an evidence-based approach to prevent suicide in emergency departments, through interactive storylines presented in the game. The game focuses on identifying warning signs, coping strategies, and resources for support with the goal to promote youth mental health and prevent the initiation or escalation of substance misuse.

5.2 Device Administration and Schedule

Eligible individuals will be assigned to either the 1) supportED group (n=30) or 2) control group (n=30). Both groups will also receive NIDA pamphlets on substance misuse for youth at the end of the session. Prior to receiving pamphlets, those in the supportED group will engage with the game for one session (~45min) while the control group will engage with a non-health-related game for the same duration. Given schools do not have a standardized approach to address suicide prevention, we opted to use an attention/time control condition. Participants will use a dedicated device (e.g., tablet, laptop, or desktop) to access their digital experience on the web. The research staff will be present to monitor gameplay, to provide support, if needed, and to field questions in person. Dedicated devices will be

prepped prior to sessions with participants (programmed as control or game). The school-based provider will be present for immediate referrals, if needed.

Currently our game does not record ANY personal information or even individual game information. We do not ask for a personal registration or login.

Twine by default does save information locally to the device running the Twine game off the Web server. No information is saved server-side and local information can be removed by deleting local-storage using the Web browser command to do so.

We envision most, if not all, players playing through an entire sitting in one session so saving locally shouldn't be a need, and devices will have local saves wiped if under-the-control of the research team.

We are considering disabling saves as well. However, Twine does maintain some saved state during play and it likely is cached (locally of course)

